| Patient population | 
53 Patients with high-risk, localized prostate cancer as defined by:
 
 1) Histologically confirmed diagnosis of adenocarcinoma of the prostate within 180 days prior to registration at very high risk of recurrence as determined by 2 or more of the following combinations: 
 a) cT3a/b b) PSA \geq20 c) Gleason score 8-10 d) \geq33% core involvement 
OR
 
any patient with pelvic lymph node involvement \geq 1 cm as determined by pelvic CT or MRI imaging will meet eligibility criteria for enrollment.
 |
| Rationale for Study | 
Long-term androgen deprivation therapy consisting of a LHRH agonist, with or without the addition of an anti-androgen, with radiation therapy improves the survival of patients with high risk prostate cancer.^{1,2} Enzalutamide is a potent anti-androgen with at least 9-fold higher binding affinity than other anti-androgens such as bicalutamide. Thus, more profound androgen deprivation therapy with the addition of enzalutamide to LHRH agonist therapy may improve the clinical outcomes of patients. The primary objective is to assess the safety, tolerability, and feasibility of the addition of enzalutamide to LHRH agonist therapy in patients with very high-risk prostate cancer or pelvic node positive disease receiving radiation therapy. Also, the potential efficacy of enzalutamide and leuprolide in combination with radiation therapy for improving the PSA complete response will be assessed.
 |
| Primary Objective | 
 1) To determine the feasibility and safety of the combination of enzalutamide and leuprolide in patients undergoing definitive radiation therapy for high-risk prostate cancer or with pelvic nodal involvement. 2) To determine the PSA complete response rate with the combination of enzalutamide and leuprolide (PSA-CR as determined by PSA nadir \leq0.3) in patients undergoing radiation therapy for high-risk prostate cancer or pelvic nodal involvement. |

| | |
|-------------------------------|---|
| 
Secondary Objectives
 | 
 1) To determine time to biochemical failure as determined by the ASTRO Phoenix definition of nadir + 2 ng/mL, local progression, regional progression, and distant metastases. 2) To determine time to clinical progression free survival 3) To assess PSA nadir and PSA and testosterone levels at 3-4, 6, 12, and 24 months. 4) To assess changes in HbA1c, fasting glucose, fasting insulin and fasting lipid and cholesterol levels. 5) To document changes in quality of life outcomes. |
| 
Correlative Objectives
 | 
 1) To identify potential mutations and changes gene copy number associated with enzalutamide resistance in patients with high risk prostate cancer. 2) To identify gene expression patterns, splice variants, and gene signatures associated with enzalutamide treatment and enzalutamide resistance in patients with high risk prostate cancer. 3) To identify changes in the immune response with enzalutamide treatment. |
| 
Study Design
 |  
Very High Risk Prostate Cancer 1. Diagnostic biopsies 2. MRI prostate*
 
Start leuprolide and Enzalutamide* (Day 0)
 
Fiducial markers# (Day 31-37)
 
Start RT (Day 53-67) 1. IMRT for 5 wks 2. Brachy boost#
 
Assess PSA-CR at Day 120
 
*Leuprolide and enzalutamide for 24 months total. *MRI– Multiparametric PET/MRI with DWI, DCE, Spectroscopy #Biopsy will be performed at time of fiducial marker placement and at time of brachytherapy boost
 
Phase II study to evaluate the safety, toxicity, and feasibility of the addition of enzalutamide to leuprolide in patients with high-risk prostate cancer or pelvic node positive disease receiving radiotherapy. High-risk prostate cancer is defined as 2 or more of the following characteristics: 1) cT3a/b, 2) PSA ≥20 and <150, 3) Gleason 8-10, and 4) ≥33% core involvement. The proportion of patients obtaining a PSA complete response at day 120 will be determined. Safety will be assessed by the National Cancer Institute Common Terminology Criteria for Adverse Events v. 4.0 criteria
 |
| 
Number of patients
 | 
53 patients. Approximately 3 patients a month are expected to be accrued with a goal complete accrual by 24 months.
 |

| | |
|-----------------------|--|
| Duration of Therapy | Patients will receive a total duration 24 months of androgen deprivation therapy including leuprolide and enzalutamide with radiation therapy. The initial phase of radiation therapy will be delivered Monday-Friday, except for holidays, for a total of 15 treatment days. The boost phase (phase 2) of radiation therapy is one day for brachytherapy. |
| Duration of Follow up | Patients will be followed for up to 36 months after completion of radiation treatment |
| Duration of study | 60 months |
| Study Treatment | Combined androgen blockade with leuprolide and enzalutamide will be administered with whole pelvic radiotherapy to a total dose of 45 Gy followed by brachytherapy boost. |
| Safety Assessments | Safety will be assessed through a summary of adverse events evaluated by NCI CTCAE v. 4.0. |

List of Abbreviations

| | |
|--------|---|
| AE | adverse event |
| ALT | alanine aminotransferase |
| AST | aspartate aminotransferase |
| ATC | Anatomical Therapeutic Chemical (Classification System) |
| AUC | area under the curve |
| CBC | complete blood cell (count) |
| CHR | Committee on Human Research (UCSF IRB) |
| CR | complete response |
| CRC | Clinical Research Coordinator |
| CRF | case report form |
| CT | computerized tomography |
| CTCEA | Common Terminology Criteria for Adverse Events |
| CTMS | Clinical Trial Management System |
| DSMC | Data and Safety Monitoring Committee |
| DSMP | Data and Safety Monitoring Plan |
| ECOG | Eastern Cooperative Oncology Group |
| FDA | Food and Drug Administration |
| GCP | Good Clinical Practice |
| HDFCCC | Helen Diller Family Comprehensive Cancer Center |
| HGB | hemoglobin |
| ICH | International Conference on Harmonization |
| IRB | Institutional Review Board |
| IV | intravenous |
| LFT | liver function test |
| MRI | magnetic resonance imaging |
| NCI | National Cancer Institute |
| PD | disease progression |
| PR | partial response |
| PRC | Protocol Review Committee (UCSF) |
| PSA | Prostate Specific Antigen |
| QOL | Quality of Life |
| SD | stable disease |
| SD | standard deviation |
| ULN | upper limit of normal |

Table of Contents

Protocol Signature Page 2

List of Abbreviations 6

Table of Contents 7

1 Background: 10

 1.1 High-Risk Prostate Cancer 10

 1.2 Enzalutamide 10

 1.3 Rationale of the Proposed Study 11

 1.4 Rationale for Correlative Studies 11

2 Objectives of the Study 12

 2.1 Primary 12

 2.2 Secondary 12

 2.3 Correlative Studies 13

 2.4 Endpoints 13

1.1 High-Risk Prostate Cancer

The majority of patients with lethal prostate cancer present with clinically localized high-risk disease and will experience disease recurrence as manifested by persistently elevated or increasing PSA levels after definitive radiation therapy. Strategies to improve the outcome of these patients with high-risk disease are an unmet need.

In patients with high-risk prostate cancer receiving radiation therapy, addition of 2-3 years of androgen deprivation therapy (ADT) is the standard of care based on phase III trials demonstrating an overall survival (OS) benefit.^{1,2,3} Five-year disease free survival (DFS) is approximately 50%. To improve outcomes, Radiation Therapy Oncology Group (RTOG) 9902 evaluated the role of adjuvant paclitaxel, estramustine, and etoposide (TEE) chemotherapy after combined androgen blockade with radiation therapy. This study failed accrual due to toxicity and did not show clinical benefit with TEE. Similarly, the GETUG-12 study evaluated the addition of docetaxel and estramustine to androgen suppression and radiation therapy in high-risk localized prostate cancer, but also did not show a significant benefit in the primary endpoint, progression free survival (PFS). Thus improvements in clinical outcome in patients with high-risk prostate cancer without added toxicity are an unmet need.

Although long-term androgen deprivation therapy improved outcomes in patients with high-risk localized prostate cancer receiving radiation, no study has evaluated the efficacy of more profound androgen blockade with enzalutamide in the same setting. Greater androgen suppression improved clinical outcomes in patients with hormone-sensitive metastatic prostate cancer. In a large phase III study, patients were randomized to greater androgen suppression with the combination of flutamide and leuprolide or to leuprolide alone. Combined androgen blockade with leuprolide and flutamide improved clinical response, PFS, and OS.⁴ The greatest benefit in OS was seen in patients with limited hormone-sensitive metastatic prostate cancer,⁴ which is the next step in progression after localized high-risk prostate cancer. Therefore, greater androgen blockade in patients with high-risk localized prostate cancer may also lead to improvements in clinical outcome.

1.2 Enzalutamide

Enzalutamide is a non-steroidal androgen receptor (AR) inhibitor. Enzalutamide inhibits the binding of androgens to the AR, inhibits the translocation of the AR to the nucleus, and inhibits AR mediated DNA binding. Enzalutamide has high affinity binding to the AR with 9-fold greater affinity than bicalutamide. Pre-clinical studies demonstrate that enzalutamide suppresses the proliferation of prostate cancer cells with AR gene amplification and can modulate the immune system to enhance immune recognition.⁵ In two phase III trials, enzalutamide was demonstrated to improve the overall survival in patients with castrate resistant prostate cancer when compared with placebo.^{6,7} Interestingly, a large proportion of patients experienced greater than 90% reduction in PSA level in these two phase III studies^{6,7} when no further reductions were expected.

Recently, enzalutamide was demonstrated to be active in men with hormone-naïve prostate cancer, with 92.5% of men experiencing a decline of $\geq 80\%$ in PSA. Approximately 25% of patients in this study had undergone radiotherapy and treatment was well tolerated.⁸

In the current study, we propose to investigate the role of more profound androgen suppression with enzalutamide in combination with an LHRH agonist in patients with high-risk prostate cancer receiving radiation therapy. Given the survival benefit with more profound androgen deprivation therapy in the hormone-sensitive setting along with the addition of 2-3 years of LHRH to radiation therapy, greater androgen blockade with the addition of enzalutamide to LHRH agonist therapy may provide an additional benefit in survival.

Enzalutamide, as demonstrated in phase II and phase III trials, is well tolerated. Adverse events that may occur with enzalutamide include fatigue, diarrhea, musculoskeletal pain, and headache. Recently, a phase II trial demonstrated safety with the addition of enzalutamide in the adjuvant setting after radiation therapy.⁸ However, no study has been reported regarding the combination of enzalutamide with LHRH agonist and concurrent radiation.

1.3 Rationale of the Proposed Study

Long-term androgen deprivation therapy consisting of a LHRH agonist, with or without the addition of an anti-androgen, with radiation therapy improves the survival of patients with high risk prostate cancer.^{1,2} Enzalutamide is a potent anti-androgen with at least 9- fold higher binding affinity than other anti-androgens such as bicalutamide. Thus, more profound androgen deprivation therapy with the addition of enzalutamide to LHRH agonist therapy may improve the clinical outcomes of patients. The primary objective is to assess the safety, tolerability, and feasibility of the addition of enzalutamide to LHRH agonist therapy in patients with very high-risk prostate cancer or pelvic node positive disease receiving radiation therapy. Also, the potential efficacy of enzalutamide and leuprolide in combination with radiation therapy for improving the PSA complete response will be assessed. We hypothesize that greater androgen blockade with addition of enzalutamide to LHRH agonist therapy will improve the PSA complete response and provide additional clinical benefit. The primary endpoint is to assess the impact of the addition of enzalutamide to LHRH agonist therapy in improving PSA complete response (PSA-CR) after radiation therapy. PSA-CR is defined as a PSA ≤ 0.3 ng/mL. This metric has been validated as a predictor of clinical outcome including disease-specific survival, distant metastasis, and biochemical failure in two large studies (RTOG 9413, n=1070; MSKCC, n=1045).^{9,10} In these studies, approximately 30% of patients failed to achieve a PSA-CR while on combined androgen blockade. Failure to obtain a PSA-CR was associated with significantly worse disease-specific survival, worse disease-free survival, higher incidence of distant metastases, and increased biochemical failure. Based on prior studies evaluating PSA response with enzalutamide, we would expect that addition of enzalutamide reduce the proportion of patients failing to achieve a PSA-CR to at least 0.15.

1.4 Rationale for Correlative Studies

Mechanisms of enzalutamide resistance including AR gene amplification, truncation mutations, gain-of-function mutations, and glucocorticoid receptor overexpression have been shown in preclinical and mCRPC patient samples. However, the mechanisms of enzalutamide resistance have not been extensively studied in patients with high-risk or pelvic node positive prostate cancer. No study has evaluated the evolution of genetic alterations through primary treatment of prostate cancer. Castration and enzalutamide resistant clones may be already present in the primary tumor in patients with very high-risk, localized disease, well before the development of metastatic disease. This is suggested by the lack of a PSA-CR in 30% of patients with high-risk disease on

androgen blockade. Further evidence comes from continued AR signaling despite combined androgen blockade in localized prostate cancer. In the current proposal, mutational analysis and gene expression/gene splicing changes leading to enzalutamide resistance will be investigated in very high-risk or pelvic node positive prostate cancer.

Recently, androgen deprivation has been shown to enhance the immune response to prostate cancer as testosterone may be immunosuppressive. Androgen ablation in a mouse model reversed T-cell tolerance to a prostate restricted tumor antigen. Also, surgical castration of mice undergoing vaccination with a prostate-specific antigen enhanced CD8 T-cell response. Lastly, in patients with prostate cancer undergoing ADT, an increase in T-cell infiltration into the prostate was observed. Thus, testosterone may suppress T-cell response to tumor antigens. The mechanisms by which androgen blockade, especially with enzalutamide, regulate the immune system will be an exploratory objective in this proposal.

In summary, the goal of the correlative studies is to identify changes associated with enzalutamide response and resistance in high-risk or node positive prostate cancer. Serial biopsies and blood collection will be obtained. Genetic mutations, gene expression changes, and immune response will be evaluated from these biopsies and blood. By integrating the information gained through serial assessment, a global view of the temporal changes within the tumor(s) is obtained. These analyses will provide insight into the mechanisms of enzalutamide resistance in the very high-risk and pelvic node positive setting. Understanding the mechanisms of enzalutamide resistance in the very high-risk and node positive setting will facilitate the selection of patients benefitting from enzalutamide treatment and the development of effective treatment regimens for a personalized treatment approach.

2 Objectives of the Study

2.1 Primary

1. To determine the feasibility and safety of the combination of enzalutamide and leuprolide in patients undergoing definitive radiation therapy for high-risk prostate cancer or with pelvic nodal involvement.
2. To determine the PSA complete response rate with the combination of enzalutamide and leuprolide (PSA-CR as determined by PSA nadir ≤ 0.3) in patients undergoing radiation therapy for high-risk prostate cancer or pelvic nodal involvement.

2.2 Secondary

1. To determine time to biochemical failure as determined by the ASTRO Phoenix definition of nadir + 2 ng/mL, local progression, regional progression, and distant metastases.
2. To determine time to clinical progression free survival
3. To assess PSA nadir and PSA and testosterone levels at 3-4, 6, 12, and 24 months.
4. To assess changes in HbA1c, fasting glucose, fasting insulin and fasting lipid and cholesterol levels.

5. To document changes in quality of life outcomes.

2.3 Correlative Studies

1. To identify potential mutations and changes gene copy number associated with enzalutamide resistance in patients with high risk prostate cancer.
2. To identify gene expression patterns, splice variants, and gene signatures associated with enzalutamide treatment and enzalutamide resistance in patients with high risk prostate cancer.
3. To identify changes in the immune response with enzalutamide treatment.

2.4 Endpoints

2.4.1 Primary Endpoint

1. The primary endpoint of the study is to determine the rate of acute toxicity (≤ 90 days within the completion of radiotherapy) and late toxicity (≥ 91 days within the completion of radiotherapy). Adverse events will be defined according to CTCAE v. 4.0 criteria. Patients will be monitored at least weekly during treatment and every 3-6 months up to 24 months and at 36 months after radiation therapy.
2. A PSA measurement will be obtained at 120-127 days after initiation of androgen deprivation therapy. The proportion of patients achieving a PSA-CR (PSA nadir ≤ 0.3) at 120-127 days will be determined. The historical proportion of patients (0.7) attaining a PSA-CR from RTOG 9413 will be utilized for comparison.

2.4.2 Secondary Endpoints

1. PSA and testosterone measurements will be made at 6 weeks and then at 3-4 months, 6 months, 12 months, 18 months, 24 months, and at 36 months as part of standard of care. The time to biochemical failure will be defined from the date of randomization to the date of a rise by ≥ 2 ng/mL from the nadir PSA per the Phoenix Definition. PSA nadir and PSA and testosterone levels will be documented at 4, 6, 12, and 24 months.
2. The time to local failure will be defined from the date of randomization to the date of biopsy proven recurrence within the prostate gland.
3. The date of regional or distant metastases will be defined as the date from randomization to the date of imaging or biopsy demonstrated evidence for recurrence in the pelvic lymph nodes (regional) or systemically. Biopsy is not required to define regional or distant metastasis; however, in absence of rising PSA, biopsy is encouraged.
4. The time to clinical progression will be defined from the date of randomization to the date of PSA failure, local failure, regional or distant metastases. Deaths prior to any of these events are treated as censoring for this endpoint.
5. Changes in HbA1c, fasting glucose, fasting insulin and fasting lipid and cholesterol levels will be assessed at 12 and 24 months during treatment.
6. Quality of life will be monitored. Changes in patient reported quality of life would be measured by the Expanded Prostate Cancer Index Composite (EPIC).

Changes in fatigue from baseline to 1 year will be measured by PROMIS. Assessment of quality adjusted survival will be performed using the EQ-5D.

2.4.3 Correlative Science Endpoints

1. To identify mutations, insertions/deletions, and changes in gene copy number associated with enzalutamide treatment and resistance, whole exome sequencing will be performed on mapped biopsies pre-enzalutamide treatment, 5-weeks post-initiation of enzalutamide therapy at the time of fiducial marker placement, and after 5 weeks of external radiotherapy. Computational analysis of raw exome data will be performed. Somatic point mutations and insertions/deletions nominated as clinically informative will be amplified and sequenced for validation.

[figure not shown]
Reads from exome sequencing of tumor and patient-matched blood cells will be aligned to target capture regions, including exons, intron/exon boundaries, and many 5' transcribed portions of promoter regions. Quality control and recalibration will be applied. To detect substitution mutations, we will use muTect (provided by [name]/[name], Broad Institute). For insertion and deletion detection, PinDel will be employed. Variant nucleotides will be merged and annotated with Annovar, followed by filtering, output, and reporting. Variant frequencies will be compared across samples as an indirect measure of non-tumor cell contamination level and abundance of mutations within the tumor cell population. Clinically informative mutations will be validated by Sanger sequencing. Tumor purity estimates from exome sequencing will be compared to estimates from tissue analyses. Tumor phylogenies will be constructed from mutations and/or copy number changes in longitudinally collected samples to understand the clonal relationships between pre and post treatment tumor biopsies.

2. To identify changes in gene expression, splice variants, and expression signatures associated with enzalutamide treatment and resistance, gene expression profiling will be performed with the Affymetrix GeneChip Human Transcriptome Array 2.0 in collaboration with GenomeDx. This array chip assesses the expression of over 1.4 million RNA features including ~22,000 known protein-coding genes as well as many thousands of non-coding RNAs. This will allow us to examine relative gene expression, splice variants, and immune response signatures.

Normalization and summarization of data will be performed using the SCAN Algorithm. Genes with at least a 2-fold difference in expression will be selected. All statistical analysis will be performed using the MultiExperiment Viewer. Principal component analysis will be performed by eigenvalue decomposition of the 3 principal components for tridimensional classification of the samples and an unsupervised hierarchical cluster by Pearson's correlation will be selected to group the samples. The significance analysis of microarrays statistical technique will be performed for descriptive and comparative purposes. We will use the R package DESeq to perform differential gene expression analysis between response and nonresponse patients. We will use the R package GoSeq to perform over- and under-representation analysis (ORA) of gene sets taking length bias into account.

- Immune response signatures will be evaluated with the Affymetrix Gene Chip Array as described above. In addition, to examine the effect on T cell subsets, T cell turnover and T cell diversity, peripheral blood will be collected at pre-enzalutamide treatment, 5-weeks post-initiation of enzalutamide therapy at the time of fiducial marker placement, after 5 weeks of external radiotherapy, and at 4 months after completion of radiation therapy. T cell diversity will be performed using deep T Cell Receptor (TCR) sequencing and T cell turnover will be assessed by evaluating the number of TCR excision circles.

3 Study Design

*Leuprolide and enzalutamide for 24 months total.

*MRI– Multiparametric PET/MRI with DWI, DCE, Spectroscopy

#Biopsy will be performed at time of fiducial marker placement and at time of brachytherapy boost

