Deep whole exome sequencing of the tumor specimens with matched germ line samples (blood) will be performed on paired samples pre- and 5 weeks post-initiation enzalutamide treatment. The results will be compared across patients that do and do not obtain a biochemical complete response. Whole exome sequencing will allow for the identification of mutations, insertions/deletions, and copy number alterations involved in enzalutamide resistance. For exome sequencing, exons will be captured in solution from one microgram of sonicated genomic DNA using an Agilent SureSelect target capture system. Libraries of captured exons will be sequenced using 75 bp paired-end sequencing on an Illumina HiSeq with a goal of 100X coverage. Libraries will be constructed with indexing to allow sequencing of 3 or more exomes/lane. Computational analysis of raw exome data will be performed as described by our group. Somatic point mutations and indels nominated as clinically informative will be amplified and sequenced for validation.

Total RNA will be extracted, amplified, fragmented, and labeled. Gene expression profiling will be performed with the Affymetrix GeneChip Human Transcriptome Array 2.0. This microarray chip assesses the expression of over 1.4 million RNA features including ~22,000 known protein-coding genes as well as many thousands of non-coding RNAs. This will allow us to examine relative gene expression, splice variants, and immune response signatures.

9 Statistical Considerations and Evaluation of Results

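### The responder versus non-responder expression comparison is assigned to DESeq, a read-count method, but the only planned expression data are SCAN-normalised array intensities

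*Combined protocol and SAP*

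**What the plan says.** Section 2.4.3 (Correlative Science Endpoints, item 2) names one expression platform: "gene expression profiling will be performed with the Affymetrix GeneChip Human Transcriptome Array 2.0 in collaboration with GenomeDx". Section 8.1.2 (Tumor biopsy) repeats it and describes array preparation: "Total RNA will be extracted, amplified, fragmented, and labeled". Pre-processing is also array-specific: "Normalization and summarization of data will be performed using the SCAN Algorithm".

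The same paragraph of section 2.4.3 then sets out the inference. The comparison by response is given to a count method: "We will use the R package DESeq to perform differential gene expression analysis between response and nonresponse patients". The gene-set step follows: "We will use the R package GoSeq to perform over- and under-representation analysis (ORA) of gene sets taking length bias into account". An array method appears as well, but without a named contrast: "The significance analysis of microarrays statistical technique will be performed for descriptive and comparative purposes". The paragraph also applies a 2-fold expression filter and states that MultiExperiment Viewer is the software for all of the statistical analysis. It gives no false-discovery level.

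The sequencing that the plan does describe is exome DNA, Sanger validation of mutations, and T-cell receptor sequencing. Section 9.4 (Analyses Plans) contains no correlative analysis, so nothing there changes section 2.4.3.

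**The concern.** DESeq fits a negative binomial model to non-negative integer read counts. Its variance is the mean plus a dispersion term, so it cannot fall below the Poisson variance. SCAN output is continuous, on a log-type scale, and can be negative. No step in the plan turns it into counts.

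GoSeq is a gene-set test, not a count model. Its special feature is a correction for longer transcripts being called differentially expressed more often because they collect more reads. Array intensities do not carry that bias in the same form.

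Correlative objective 2 asks for expression patterns and signatures of enzalutamide treatment and resistance. The DESeq comparison is the only test that the plan ties to response. If it cannot be run as specified, the analyst must improvise a transformation or a replacement method, possibly after seeing the data. Non-responders are expected to be few, so a choice that wastes power matters.

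**Working it through.** **1. Data type against method.** The documents give no sample size, power or alpha for this analysis, so there is no stated figure to reproduce.

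| Step in the plan | Data it yields or needs |
|---|---|
| Affymetrix array (2.4.3, 8.1.2) | yields probe intensities |
| SCAN (2.4.3) | yields continuous log-type values |
| DESeq (2.4.3) | needs integer counts |
| GoSeq length correction (2.4.3) | presumes read-count length bias |
| SAM (2.4.3) | suits array values |

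No planned assay supplies RNA read counts to rows three and four.

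**2. Inputs for an illustration.**
- From the documents: 53 patients; PSA-CR rates of 70% (historical) and 85% (expected), section 9.2.1; the 2-fold filter, section 2.4.3.
- Non-responders: 53 × 0.15 = 7.95, about 8 (8 v 45); 53 × 0.30 = 15.9, about 16 (16 v 37). This takes response to mean PSA-CR and assumes usable RNA from every patient.
- Assumed, not in the documents: normal log2 intensities, mean 8, SD 0.4 to 1.0; a 2-fold change is +1 on the log2 scale in non-responders.

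**3. Why rounding log2 values removes power.** For 8 v 45, group means of 8 and 9 treated as counts differ by ln(9/8) = 0.118. The smallest standard error that the model allows is √[(1/8)/45 + (1/9)/8] = 0.129, so z = 0.118/0.129 = 0.91. For 16 v 37 the standard error is 0.102 and z = 1.16. Both are well short of 1.96. The model takes the variance to be about 8, when the true variance is 0.16 to 1.0.

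On the log2 scale, the same change for 8 v 45 gives 1/(SD × √(1/8 + 1/45)) = 1/(SD × 0.384). That is 6.5 at SD 0.4 and 2.6 at SD 1.0.

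**4. Simulation.** One gene, 4,000 runs per setting, two-sided 0.05. A two-group negative binomial Wald test with moment dispersion stands in for DESeq; it is not the package. Entries are rejection rates for a true 2-fold change.

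| Groups | SD | Rounded log2, count model | Back-transformed and rounded, count model | t-test on log2 |
|---|---|---|---|---|
| 8 v 45 | 0.4 | 0.000 | 1.000 | 1.000 |
| 8 v 45 | 0.7 | 0.000 | 0.941 | 0.962 |
| 8 v 45 | 1.0 | 0.002 | 0.636 | 0.728 |
| 16 v 37 | 0.4 | 0.000 | 1.000 | 1.000 |
| 16 v 37 | 0.7 | 0.001 | 0.994 | 0.997 |
| 16 v 37 | 1.0 | 0.011 | 0.857 | 0.918 |

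With no true difference, the rejection rates were 0.000 in every setting for rounded log2 values, 0.049 to 0.057 for back-transformed values, and 0.041 to 0.053 for the t-test. None of these has a multiplicity adjustment.

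**The case against.** The strongest reply is that little harm would follow. DESeq cannot take SCAN values directly, so the likely outcome is a visible failure and a respecified method, not a silently wrong result. The near-total loss of power arises only if log2 values are rounded, which the plan does not propose. The back-transformed route performs tolerably. SAM is already named, suits arrays and is built around false-discovery estimation. The endpoint generates hypotheses and has no alpha, power or decision attached. Objective 2 also covers treatment-associated expression and splice variants, and the plan lists principal components and clustering.

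Much of this stands. It limits the consequence to an analysis that cannot be executed as written and an open choice for the analyst. It does not remove the mismatch. The text gives the response contrast to DESeq and not to SAM, and it states no transformation.

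A reader might also infer a flood of false positives: 5% of about 22,000 protein-coding genes is 1,100. The documents do not support that figure. Rounded log2 values make the count model conservative (null rejection 0.000). The 2-fold filter would, if applied to this contrast, remove most null genes: at 8 v 45 a null gene would need a deviation of 6.5 standard errors at SD 0.4, or 2.6 at SD 1.0. SAM and DESeq can both report FDR; what is missing is a stated level.

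**Conclusion.** The point holds in a limited form. The plan assigns the response contrast to a read-count method when its only expression data are continuous array values. Running it needs an undescribed transformation, and that choice alone can move power for a 2-fold change from nearly zero (0.000 to 0.011) to 0.64 to 1.00. GoSeq's length correction has no clear basis here. SAM is suitable but unassigned, and naming a single program for all analysis conflicts with the two R packages in the same paragraph.

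The power figures are illustrations. They depend on the assumed mean and SDs, a stand-in for DESeq, and RNA from all 53 patients. Table 6 makes the TRUS biopsies optional and archival tissue is collected only if available, so the usable number is unknown and could be smaller.

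A reader might infer that the expression p-values would be invalid in every case, or that the trial's main conclusions are at risk. Neither follows. One workable transformation kept size near nominal, and the PSA-CR and toxicity analyses in section 9.4.2 do not use these data. The effect is confined to correlative objective 2.

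**What to change.** In section 2.4.3:

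- Assign the response versus non-response comparison to SAM, which is already named, or to a moderated linear model such as limma, applied to the SCAN values. State the FDR level and define response (for example, PSA-CR at the primary time point).
- Replace GoSeq with a gene-set test suited to array data, such as camera or GSEA.
- Reconcile the MultiExperiment Viewer sentence with whatever R packages remain.

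If RNA sequencing is in fact intended, say so in sections 2.4.3 and 8.1.2. DESeq and GoSeq could then stay, and SCAN and the array would need to be reconciled with them.

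Correcting the methods costs a few sentences, uses free software and needs no new data or patients. The change should be made before response status is linked to the expression data. Moving to RNA sequencing would be a change of assay, with its own cost.
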